1.3 Study Overview

This study is being conducted to gain safety and efficacy information on the long-term use of rVIII-SingleChain in subjects with severe hemophilia A in addition to data from previous lead-in clinical studies. This study also aims to collect information on inhibitor formation in PUPs 0 to < 18 years of age. The EMA guideline entitled “Guideline on the clinical investigation of recombinant and human plasma-derived factor VIII products”, adopted 21 July 2011, requires the collection of “...additional clinical data to ensure consistency in the long-term between the outcome from pre-authorization clinical studies and from routine use...”, necessitating a post-marketing investigation study. With reference to PUPs, the guideline in effect in 2011 states that “approval of the indication in PUPs will be based on a clinical trial in a minimum of 50 PUPs evaluated for efficacy and safety during at least 50 EDs” [EMA, 2011]. Thus, in line with the EMA guideline in effect at time of study planning and implementation of Amendment 3, this extension study was planned to a) fulfill the EMA requirements for a post-marketing investigation to attain 100 EDs in at least 200 PTPs (completed) and b) acquire efficacy and safety data in at least 50 PUPs attaining at least 50 EDs to rVIII-SingleChain. For PTPs directly rolling over from any of the preceding rVIII-SingleChain clinical studies, EDs for rVIII-SingleChain are calculated from the first dose of rVIII-SingleChain, including all EDs to rVIII-SingleChain from any study or substudy.

CCI

The EMA guideline has since been updated in 2018 and states “In light of increasing scientific knowledge [Gouw et al., 2013; Calvez et al., 2014; Collins et al., 2014; Peyvandi et

al., 2016], the number of suitable patients especially previously untreated patients (PUPs) to be enrolled in clinical trials is problematic. Hence, the conduct of sufficiently informative clinical trials in PUPs to estimate important characteristics of single products is considered difficult. Therefore the obligation to perform clinical trials in PUPs for marketing authorisation purposes has been deleted [EMA, 2108].” CSL Behring has reached an agreement with the EMA Paediatric Committee through a request for modification of the pediatric investigational plan (PIP) to stop enrolling subjects into Study CSL627_3001 and to continue treatment of the subjects currently enrolled. In addition, to ensure that patients achieve PTP status at the end of participation in Arm 2, all PUPs were to achieve 150 EDs to rVIII-SingleChain. However, based on a recently published report of risk periods for inhibitor development in 1038 PUPs with severe hemophilia A, there is now strong evidence from the largest prospective cohort study of PUPs to show that almost all inhibitors have developed by 75 EDs of treatment [Van den Berg et al., 2019]. CCI [REDACTED]

The study population will consist of a total of at least 224 subjects with severe hemophilia A (FVIII activity level of < 1%). Of these, at least 200 are PTPs who have participated in a previous CSL-sponsored study with rVIII-SingleChain (ie, Arm 1) or who are not currently enrolled in a rVIII-SingleChain study (Arm 3), and at least 24 are PUPs (ie, Arm 2).

In line with the EMA guideline, Arm 2 of the present study was opened for enrollment after the following information became available:

- a) Independent Data Monitoring Committee (IDMC) approval that the data from at least 20 PTPs < 12 years of age with 50 EDs each (including at least 10 PTPs 0 to < 6 years of age and at least 10 PTPs 6 to < 12 years of age) in Study CSL627_3002 does not reveal any safety concern.
- b) The rVIII-SingleChain PK in children is adequately characterized from Study CSL627_3002.

In addition, Arm 3 remained closed until the sponsor determined to open it. Arm 3 was opened in order to achieve a total of at least 200 PTPs for 100 EDs in Arms 1 and 3 combined. The sponsor contacted investigators directly when Arm 3 was open for enrollment.

rVIII-SingleChain will be administered intravenously (IV) at an actual dose and on a dosing schedule at the investigator’s discretion. This study will be conducted in compliance with this

study protocol, International Conference of Harmonisation (ICH) principles of Good Clinical Practice (GCP), and the applicable regulatory requirement(s) (see [Section 13.1](#)).

1.4 Potential Risks and Benefits

The risks include the possibility that subjects treated with rVIII-SingleChain may develop an inhibitor and that antihemophilic factors may therefore be less effective or ineffective in increasing FVIII levels and stopping or preventing bleeding. Treatment with any antihemophilic factor presents a risk of inhibitor formation particularly in PUPs in which the risk of inhibitor formation has been estimated to be up to 35.4% [SIPPET study, [Peyvandi et al., 2016](#); [Kasper, 2004](#)]. The development of an inhibitor is associated with significant morbidity and mortality, including a higher rate of bleeding complications, increased disability and a decreased quality of life [[Witmer and Young, 2013](#)]. The absolute risk of inhibitor formation with rVIII-SingleChain is currently unknown. In Study CSL627_1001 in 174 PTPs with previous exposure to > 150 EDs to FVIII products, 120 subjects achieved ≥ 50 EDs, of whom 52 subjects had ≥ 100 EDs to rVIII-SingleChain at the end of the study.

CCI [Redacted]

CCI [Redacted]

For subjects in all study arms, the potential benefits of treatment include stopping and / or preventing bleeding. In addition, rVIII-SingleChain has demonstrated an adequate safety profile for PTPs. The associated benefit-risk assessment of the study is acceptable for subjects enrolled.

Please refer to the Investigator’s Brochure for more detailed information.

2 Study Objectives and Endpoints

Overall, the study objectives in all 3 study arms are to gain additional safety information on the incidence of FVIII inhibitors (including in PUPs), frequency of adverse events (AEs), and serious AEs (SAEs) associated with the use of rVIII-SingleChain, and to gain additional information on the efficacy of rVIII-SingleChain in PTPs and PUPs with severe hemophilia A. This study will collect information on subjects undergoing surgery during the study, thereby providing information on the safety and efficacy of rVIII-SingleChain during surgery. CCI

[REDACTED]

2.1 Primary Objective and Endpoint

2.1.1 Primary Objective

In **Arms 1 and 3 (PTPs)**, the primary objective is to characterize the long-term safety profile of rVIII-SingleChain with respect to inhibitor development in PTPs.

In **Arm 2 (PUPs)**, the primary objectives are:

- To characterize the safety with respect to inhibitor development in PUPs.
- To evaluate the efficacy of on-demand and prophylaxis treatment of rVIII-SingleChain in PUPs.

2.1.2 Primary Endpoints

In **Arms 1 and 3 (PTPs)**, the primary endpoint is the incidence of inhibitor formation to FVIII in at least 200 PTPs with at least 100 EDs of rVIII-SingleChain.

In **Arm 2 (PUPs)**, the primary endpoints are:

- Incidence of high-titer inhibitor formation to FVIII (ie, inhibitor titer of ≥ 5 Bethesda units [BU]/mL) in PUPs with at least 50 EDs of rVIII-SingleChain.
- Treatment success for **major** bleeding episodes, defined as a rating of "excellent" or "good" on the investigator's clinical assessment of hemostatic efficacy 4-point scale.
- Annualized spontaneous bleeding rate (AsBR) during prophylaxis and on-demand treatment.

2.2 Secondary Objectives and Endpoints

2.2.1 Secondary Objectives

In **Arms 1 and 3 (PTPs)**, the secondary objectives are:

- To characterize the safety profile of rVIII-SingleChain with respect to inhibitor development after 10 EDs and after 50 EDs.
- To characterize the safety profile of rVIII-SingleChain with respect to antibodies against rVIII-SingleChain and antibodies to Chinese hamster ovary (CHO) proteins.
- To collect and evaluate efficacy information on the prophylaxis and treatment of bleeding episodes.
- To assess the hemostatic efficacy of rVIII-SingleChain for PTPs who undergo surgery, using the 4-point efficacy evaluation of surgical treatment scale.

In **Arm 2 (PUPs)**, the secondary objectives are:

- To further characterize the safety profile of rVIII-SingleChain with respect to inhibitor development.
- To characterize the safety profile of rVIII-SingleChain with respect to antibodies against rVIII-SingleChain, and antibodies to CHO proteins.
- To collect and evaluate the number of rVIII-SingleChain injections required for the treatment of bleeding episodes.
- To characterize consumption of rVIII-SingleChain in prophylaxis, on-demand treatment, and surgery.
- To assess the hemostatic efficacy of rVIII-SingleChain for PUPs who undergo surgery, using the 4-point efficacy evaluation of surgical treatment scale.
- To assess the occurrence of clinically significant abnormalities in vital signs after rVIII-SingleChain administration.

2.2.2 Secondary Endpoints

2.2.2.1 Efficacy

In **Arm 1 and Arm 3 (PTPs)**, the secondary efficacy endpoints are:

- Annualized bleeding rate (ABR) (traumatic and non-traumatic) during prophylaxis and on-demand treatment.
- Treatment success for bleeding episodes defined as a rating of "excellent" or "good" on the investigator's clinical assessment of hemostatic efficacy 4-point scale.

- Percentage of bleeding episodes requiring 1, 2, 3, or > 3 injections of rVIII-SingleChain to achieve hemostasis.
- Mean actual dose per kg per subject per year; consumption of rVIII-SingleChain, expressed as number of injections and IU/kg per month and per year, as well as IU/kg per event (prophylaxis, on-demand, and surgery).
- Treatment success for surgery, using the 4-point efficacy evaluation of surgical treatment scale.

In **Arm 2 (PUPs)**, the secondary efficacy endpoints are:

- Treatment success for **non-major** bleeding episodes, defined as a rating of "excellent" or "good" on the investigator's clinical assessment of hemostatic efficacy 4-point scale.
- Percentage of bleeding episodes requiring 1, 2, 3 or > 3 injections of rVIII-SingleChain to achieve hemostasis.
- ABR during prophylaxis and on-demand treatment.
- Mean actual dose per kg per subject per year; consumption of rVIII-SingleChain, expressed as number of injections and IU/kg per month and per year, as well as IU/kg per event (prophylaxis, on-demand, and surgery).
- Treatment success for surgery, using the 4-point efficacy evaluation of surgical treatment scale.

2.2.2.2 Safety

In **Arm 1 and Arm 3 (PTPs)**, the secondary safety endpoints are:

- Incidence of inhibitor formation to FVIII in at least 200 PTPs after 10 EDs and after 50 EDs with rVIII-SingleChain.
- Percentage of PTPs who develop antibodies against rVIII-SingleChain.
- Percentage of PTPs who develop antibodies to CHO proteins.

In **Arm 2 (PUPs)**, the secondary safety endpoints are:

- Incidence of high-titer inhibitor formation to FVIII (ie, inhibitor titer of ≥ 5 BU/mL) after 10 EDs with rVIII-SingleChain in PUPs.
- Incidence of low-titer inhibitor formation (ie, inhibitor titer of < 5 BU/mL) to FVIII after 10 EDs and after 50 EDs with rVIII-SingleChain in PUPs.
- Incidence of total (low- and high-titer) inhibitor formation to FVIII after 10 EDs and after 50 EDs with rVIII-SingleChain in PUPs.
- Percentage of PUPs who develop antibodies against rVIII-SingleChain.

- Percentage of PUPs who develop antibodies to CHO proteins.
- Percentage of PUPs with clinically significant abnormal values for blood pressure, or heart rate, or body temperature at 1, 2, 3, or 6 hours after the first rVIII-SingleChain injection.
- Percentage of PUPs with treatment-emergent clinically significant abnormal values for blood pressure, heart rate, or body temperature during the course of the study.

2.3

CCI [Redacted]

2.3.1

CCI [Redacted]

2.3.2

CCI [Redacted]

CCI [Redacted]

CCI

2.4 Safety Variables Assessed

In all study arms, the following routine safety variables will be assessed:

- Frequency, severity and seriousness of AEs.
- Laboratory values over time, individual subject changes, and clinically significant abnormal values.
- Vital signs values over time, individual subject changes, and clinically significant abnormal values.
- Physical examination.
- Subject / caregiver assessment of local tolerability.

In **Arm 2 and Arm 3 only**, the following will be assessed in addition:

- Investigator assessment of local tolerability (for rVIII-SingleChain injections administered at the clinic).

[figure not shown]
CCI

3 Study Design

3.1 Study Design and Rationale

This multicenter, non-randomized, open-label, multiple-arm phase 3 extension study will continue to investigate the safety and efficacy of rVIII-SingleChain in PTPs with severe hemophilia A as well as in PUPs. This study will evaluate the prophylaxis and on-demand treatment of bleeding episodes in at least 200 PTPs who achieve at least 100 EDs as well as in PUPs who achieve at least 50 EDs. A surgical substudy (open to subjects from all study arms) will investigate the use of rVIII-SingleChain in surgery. CCI

[figure not shown]
Eligible subjects will be males who have been diagnosed with severe hemophilia A (FVIII activity levels < 1%). Subjects in Arms 1 are PTPs of any age who have participated in a previous CSL-sponsored clinical study with rVIII-SingleChain. Subjects in Arm 2 are PUPs

0 to < 18 years of age who have not participated in any clinical study with rVIII-SingleChain and have no other prior exposure to any FVIII product. Subjects in Arm 3 are PTPs 0 to < 65 years of age previously exposed to FVIII products (which may include rVIII-SingleChain) but who are not currently enrolled in a rVIII-SingleChain study.

Arm 2 PUPs can enter this study either at the time of their first bleeding episode or previously diagnosed with hemophilia A in a non-bleeding state.

This study is designed to collect data on the use of rVIII-SingleChain to assess long-term safety and efficacy beyond the outcome from pre-authorization clinical studies as well as to assess inhibitor development and characterize efficacy and safety of rVIII-SingleChain in PUPs. Inhibitor development is of particular interest for the safety of rVIII-SingleChain.

[figure not shown]
Figure 1: Study Overview of CSL627_3001

Abbreviations: ED = exposure day; PTP = previously treated patient; PUP = previously untreated patient.
A: Estimated duration of study participation to achieve the indicated number of EDs to rVIII-SingleChain.
B: All subjects who participate in Study CSL627_3001 are eligible for the surgery substudy at any time during the study.

CCI

Figure 2: Disposition Plan for PUPs

Abbreviations: CCI; PUP = previously untreated patient.

3.2 Dose and Dosing Regimen

In all study arms, the investigator will assign subjects to prophylaxis or on-demand treatment regimens.

3.2.1 Prophylaxis Treatment Regimen

In previous studies, most subjects received prophylaxis treatment with an initial range of 15 to 50 IU/kg rVIII-SingleChain every second day or 2 to 3 times per week. In all study arms, the dose prescribed will be based on the subject's weight at the most recent visit. All subjects will be dosed according to the actual potency printed on the vial label and will be treated by IV injection.

- In Arms 1 and 3 (PTPs), the investigator will determine the rVIII-SingleChain dose and dosing schedule for the subject based upon the subject's PK profile, rVIII-SingleChain

PK data, previous FVIII treatment regimen, bleeding phenotype (if available), and taking into consideration the WFH guidelines [WFH, 2012].

- In **Arm 2 (PUPs)**, the investigator will determine the rVIII-SingleChain dose and dosing schedule at their discretion, taking into consideration the WFH guidelines [WFH, 2012], subject's age and other disease characteristics (eg, bleeding phenotype).

3.2.2 Treatment of Bleeding Episodes in Subjects on Prophylaxis and in Subjects On-Demand Treatment Regimens

In the event of a bleeding episode, subjects will be treated at a dose pre-determined by the investigator based on the type and severity of the bleeding episode. All subjects should treat bleeding episodes with rVIII-SingleChain when they occur, regardless of the assigned treatment regimen. The desired FVIII level for the treatment of a bleeding episode (on-demand treatment) is based on the recommendations of the WFH [WFH, 2012].

All subjects will be dosed according to the actual potency printed on the vial label and will be treated by IV injection.

3.2.3 Preventive and Additional Doses

In all study arms, preventive doses of rVIII-SingleChain are allowed. A preventive dose is defined as a dose that is taken prior to an activity or a minor procedure to prevent or minimize a bleeding episode.

In all study arms, additional doses of rVIII-SingleChain are allowed. An additional dose is defined as a dose that is taken beyond the need to control hemostasis and does not contribute to the efficacy evaluation of the bleeding episode. These preventive and additional doses will not contribute to the efficacy evaluation of the bleeding episode but should be captured in the subject's electronic diary (eDiary) or electronic case report form (eCRF), if administered in the hospital. Preventive and additional doses will contribute to EDs and consumption data.

3.2.4 Surgery Doses

In all study arms, the investigator will determine the rVIII-SingleChain dose and treatment schedule for a subject who is scheduled for surgery based on the type of surgery and the clinical status of the subject. The PK data of the study subject or population (if available) will be utilized for calculating the dose regimen of rVIII-SingleChain before, during and after surgery to achieve and maintain the FVIII activity level recommended by the WFH Guidelines [WFH, 2012].

A subject who is required to have surgery during the study will be treated with rVIII-SingleChain before surgery, during surgery, and after surgery, under the supervision of and as prescribed by the treating physician. The subject's normal study routine will be temporarily suspended for the duration of the surgery substudy and the subject will return to the normal study routine after he is determined to be hemostatically stable following surgery as determined by the investigator. Start and end date of the surgical period should be documented in the eCRF.

3.2.5 Change in Treatment Regimens and Dose Modifications

In all study arms, changes in treatment regimens (on-demand or prophylaxis) and dose modifications are allowed and will be permitted at the investigator's discretion. The timing of dose adjustment should be flexible and based on the type of bleeding episode, the location of the bleeding episode, the age of the patient, and bleeding phenotype. The eCRF should be updated accordingly for each change in treatment regimen. Compliance with the assigned dose regimen will be assessed using the criteria detailed in [Section 6.2.4](#).

Special considerations for Arm 2 (PUPs):

- Arm 2 PUPs **switching from on-demand to prophylaxis** during the treatment period should have monthly visits until 25 EDs, followed by visits every 3 months until End of Study.
- Arm 2 PUPs **switching from prophylaxis to on-demand** during the treatment period will have follow-up visits 1 month after each rVIII-SingleChain dose (see [Section 8.10.2](#) for details).

3.2.6

CCI

CCI

3.3 Planned Study Duration

The duration of the study for an individual subject is expected to be approximately 6 years to achieve the following number of EDs with rVIII-SingleChain:

- PTPs in Arm 1 may enroll immediately after participation in previous rVIII-SingleChain studies and continue treatment until achieving at least 100 EDs (including EDs from any previous rVIII-SingleChain study).

- Inhibitor-negative PUPs in Arm 2 will receive treatment in this study until they achieve 75 EDs with rVIII-SingleChain; the overall study duration is expected to be up to 6 years. Additional time of up to 3 years in the study may occur for PUPs that develop an inhibitor:
 - CCI [REDACTED]
 - For inhibitor-positive PUPs who remain in the **main study** who have achieved eradication, the End of Study Visit will occur when they complete the 12-month post eradication follow-up period in the main study. The maximum duration of the inhibitor treatment period is 24 months starting when the dose is initially adjusted to treat the inhibitor, and if no dose adjustment is performed to treat the inhibitor then the duration of inhibitor treatment will be from the date of inhibitor diagnosis.
- PTPs in Arm 3 will receive treatment in this study until they achieve at least 100 EDs with rVIII-SingleChain (excluding EDs from any previous rVIII-SingleChain study that the subject may have participated in).

In all study arms, subjects will complete the study as outlined in [Section 3.1](#) or until the study is terminated by the sponsor.

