11.3.2.1 Primary Efficacy Analysis

For **Arms 1 and 3 (PTPs)**, there is no primary efficacy endpoint.

For **Arm 2 (PUPs)**, the analyses of the primary efficacy endpoints are outlined below:

- The investigator's clinical assessment of hemostatic efficacy for the treatment of **major** bleeding episodes, based on the 4-point ordinal scale (excellent, good, moderate, poor / no response), will be tabulated. The percentage of major bleeding episodes treated successfully (defined as ratings of excellent or good) will be summarized, and reported together with a two-sided 95% CI. To estimate the proportion, the denominator will include all treated bleeding episodes categorized as major. To account for within-subject correlation, generalized linear modeling using SAS' GENMOD procedure will be utilized. The model will contain only the intercept term. The binomial distribution with logit link function will be specified.
- The AsBR will be derived for each subject as follows: ((number of spontaneous bleeding episodes) / (observed treatment period of interest))*365.25. The AsBR will be summarized by regimen (on-demand or prophylaxis) using descriptive statistics. In addition, the number of spontaneous bleeding episodes per year and associated 95% CI will be estimated based on a Poisson model. Generalized linear modeling using SAS' GENMOD procedure will be utilized. The Poisson distribution with log link function, and log_time offset will be specified. The Poisson-based number of spontaneous bleeding episodes per year will be presented by regimen (on-demand or prophylaxis).

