### 3.2.2 On-demand Treatment Regimen

Subjects assigned to the on-demand treatment regimen will treat themselves or be treated by a caregiver/guardian as needed for any bleeding episode. For the on-demand treatment of bleeding episodes, the initial treatment dose and subsequent dose(s) to achieve hemostasis will be recorded, as well as confirmation that the subject received product and was given instruction for proper use.

After each bleeding episode, the number of injections required to achieve hemostatic efficacy with rVIII-SingleChain will be documented by the subject/caregiver/guardian. The details of each bleeding episode (e.g., type, location, and severity), treatment dose per event, and time required for improvement/resolution of symptoms will be recorded.

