## 4.5 Exposure

### 4.5.1 Exposure Days and Time on Study

Exposure days (EDs) and time on study will be summarized for the Safety, Efficacy, Surgery and CCI population. Exposure for subjects coming from the pivotal studies (1001, 3002) will also be assessed cumulatively.

An ED is defined as any day that the subject receives an injection of rVIII-SingleChain regardless of the number of injections on that day. Total EDs are cumulative from previous pivotal study for PTPs in Arm 1 and are calculated from the first dose of rVIII-SingleChain, including all EDs to rVIII-SingleChain from any study or the surgical component of this study.

CCI

The number of EDs will be summarized as both a continuous and categorical variable by age group as defined in this section.

The following categories will be presented, based on first day of dosing in the pivotal study for Arm 1 and in this study for Arm 2 and Arm 3:

- PTPs: 0-10 EDs, >10-15 EDs, >15-50 EDs, >50-75 EDs, >75-100 EDs, >100 EDs
- PUPs: 0-10 EDs, >10-25 EDs, >25-50 EDs, > 50 EDs

Exposure days in the current study will be summarized as well, as both a continuous and categorical variable as described above. EDs in the current study are counted from first dose in this study or the surgical component of this study or the CCI [REDACTED]

Total time on study (days) will be derived as:

$[Maximum \text{ (rVIII-SingleChain last dose date, End of study visit date)}] - [Minimum \text{ (rVIII-SingleChain first dose date considering pivotal study for PTPs Arm 1, Day 1 date in the current study)}] + 1.$

Time on current study (days) will be derived as:

$[Maximum \text{ (rVIII-SingleChain last dose date, End of study visit date)}] - [Minimum \text{ (rVIII-SingleChain first dose date during the current study, Day 1 date in the current study)}] + 1.$

Total time on study and time on current study in days, weeks (days/7), and months (days/30.4375) will be summarized using descriptive statistics. Time on study will be described with statistics for continuous variables. Total subject-years will be provided.

CCI [REDACTED]

ED will also be summarized by Inhibitor Level (high/low titer) on PUPs.

In addition, a separate exposure analysis over the period of inhibitor development will be provided while subjects are inhibitor positive on PUPs.

CCI [REDACTED]

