### AsBR

AsBR will be derived by inhibitor status and overall as follows:

$$(\text{number of bleeding events}) / (\text{observed treatment period of interest days}) * 365.25.$$

Only bleeding events requiring treatment will be included in the derivation of bleeding rates. The AsBR will be estimated for subjects who complete at least 8 weeks of treatment on the given inhibitor status using the subject's observed data. If the subject does not complete at least 8 weeks of treatment on the given inhibitor status, then the AsBR will be considered missing.

The number of spontaneous bleeding episodes per year based on a Poisson model and associated 95% CI and the number and percentage of subjects with zero bleeding episodes will be presented. In addition, the rate ratio of Prophylaxis modality to On-Demand modality (Prophylaxis- On-Demand) will be presented, along with the associated 95% CI, as obtained by the Poisson model.

Spontaneous bleeding episodes are those classified as 'Non-traumatic' in e-Diary or 'Spontaneous' in the eCRF. Annualized spontaneous bleeding rate will also be summarized for the following subgroup:

- Positive non-inhibitory Anti-Drug Antibodies (ADAs) and negative during the study
- Age based on age in this study: for PTPs: 0 to < 6 years,  $\geq 6$  to < 12 years,  $\geq 12$  to < 18 years and  $\geq 18$  to  $\leq 65$  years, 0 to <12 years,  $\geq 12$  to  $\leq 65$  years.
- Prophylaxis frequency: every second day, 3 times per week, 2 times per week, other regimen.

In these subgroup analyses rate ratio of Prophylaxis modality to On-Demand modality won't be displayed.

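### When boys differ in bleeding rate, the 75-ED exit in Arm 2 makes the pooled Poisson model tend to understate the mean per-boy on-demand AsBR and pull the prophylaxis/on-demand ratio towards 1

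*Protocol*

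**What the plan says.** - **Exit.** Protocol 3.3: "Inhibitor-negative PUPs in Arm 2 will receive treatment in this study until they achieve 75 EDs with rVIII-SingleChain". Protocol 8.10.6 repeats the 75-ED end of study for inhibitor-negative boys. Protocol 3.3 adds that "the overall study duration is expected to be up to 6 years", and for inhibitor-positive boys: "Additional time of up to 3 years in the study may occur for PUPs that develop an inhibitor".
- **What counts as an ED.** SAP 4.5.1: "An ED is defined as any day that the subject receives an injection of rVIII-SingleChain regardless of the number of injections on that day".
- **Where on-demand EDs come from.** SAP 3.2.2: "Subjects assigned to the on-demand treatment regimen will treat themselves or be treated by a caregiver/guardian as needed for any bleeding episode". Protocol 3.2.3 adds a smaller source: "Preventive and additional doses will contribute to EDs and consumption data".
- **Time at risk.** Under SAP 4.6 the efficacy evaluation period closes at the End of Study Visit or the last dose, whichever is later, so the denominator inherits the exit rule.
- **Analysis.** Protocol 11.3.2.1 derives AsBR for each subject and summarises it descriptively by regimen. It then adds a model-based rate with a 95% CI: "The Poisson distribution with log link function, and log_time offset will be specified". SAP 4.6.1.1 (AsBR) adds that "the rate ratio of Prophylaxis modality to On-Demand modality (Prophylaxis- On-Demand) will be presented", with a CI from the same model. The GENMOD code in SAP 4.13 lists subject as a class variable but has no REPEATED statement, dispersion term or subject effect.

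**The concern.** AsBR is a primary efficacy endpoint for Arm 2. If follow-up shortens as bleeding rises, a rate formed from pooled bleeds over pooled time is weighted towards the boys who bleed least. Prophylaxis boys collect EDs mainly by schedule, so the distortion falls almost wholly on the on-demand group and carries into the ratio.

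This differs from the usual overdispersion comment. A scale factor, or GEE with independent working correlation, would widen the interval around the same low estimate. The report could also show a descriptive mean and a lower Poisson rate for the same group, with nothing in the plan to say which to rely on.

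**Working it through.** The documents give no event rate, effect size or sample-size calculation for AsBR, so there is no planned figure to reproduce.

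**From the documents:** exit at 75 EDs; expected duration up to 6 years; a Poisson model with a log-time offset.

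**Assumed:** 6 to 30 treated bleeds a year on demand, 1.5 EDs per bleed, half of bleeds spontaneous, gamma-distributed rates between boys with CV 0 to 0.8, and 6 years treated as a limit.

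**1. What the model estimates.** Within a regimen the fit gives Σ bleeds / Σ time, which tends to E[λT]/E[T]. On demand, T ≈ min(75/(d × λ), 6), where λ is treated bleeds per year and d is EDs per bleed. If the 75-ED rule ends follow-up for everyone, λT is constant and the pooled rate becomes the harmonic mean, 1/E[1/λ]. For gamma rates with CV below 1 that is mean × (1 − CV²): 0.91 of the mean at CV 0.3 and 0.75 at CV 0.5.

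**2. Two boys.** Take 10 and 40 treated bleeds a year at 1.5 EDs per bleed.
- Follow-up: 75/(1.5 × 10) = 5.0 years and 75/(1.5 × 40) = 1.25 years, both inside 6 years.
- Pooled rate: (50 + 50)/(5.0 + 1.25) = 16.0.
- Mean of the two rates: (10 + 40)/2 = 25.0.
- At 1 ED per bleed the lighter bleeder reaches the 6-year limit and the heavier leaves at 75/40 = 1.875 years: (60 + 75)/(6 + 1.875) = 17.1.

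**3. When time, not EDs, ends follow-up.** 75/6 = 12.5 EDs a year, or 12.5/1.5 ≈ 8.3 treated bleeds a year. Below that the bias is small.

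**4. Simulation.** Pooled Poisson AsBR divided by the true mean AsBR, large groups, 1.5 EDs per bleed, 6-year limit:

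| Bleeds/year | CV 0 | CV 0.3 | CV 0.5 | CV 0.8 |
|---|---|---|---|---|
| 6 | 0.999 | 0.989 | 0.957 | 0.878 |
| 12 | 0.999 | 0.930 | 0.855 | 0.732 |
| 20 | 1.001 | 0.913 | 0.794 | 0.634 |
| 30 | 1.000 | 0.911 | 0.770 | 0.571 |

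In the same cells the mean of per-boy AsBR was 1.000 to 1.021 of truth, and a negative binomial fit with the same offset was 0.981 to 1.003.

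**5. At a plausible Arm 2 size.** With 12 on-demand boys and the 8-week minimum, CV 0.3 to 0.8:

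| Bleeds/year | Pooled/true |
|---|---|
| 6 | 0.87 to 1.00 |
| 20 | 0.66 to 0.92 |
| 30 | 0.59 to 0.92 |

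In this run the per-boy mean was 0.99 to 1.05 of truth and the negative binomial 0.93 to 1.01.

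**6. The ratio.** On prophylaxis, 75 EDs take 75/2 = 37.5 weeks at two doses a week or 75/3 = 25 weeks at three, largely whatever the bleeding. Assume 3 treated bleeds a year on prophylaxis (CV 1) against 20 on demand. The pooled prophylaxis rate is then 0.96 to 0.98 of truth, and a true ratio of 0.15 is estimated as:

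| On-demand CV | Estimated ratio |
|---|---|
| 0 | about 0.145 |
| 0.3 | 0.16 |
| 0.5 | 0.18 to 0.19 |
| 0.8 | 0.22 to 0.23 |

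**The case against.** A reader might infer that the on-demand rate will be understated whatever the data, or that the whole primary endpoint is biased. The documents support neither. With no spread between boys there is no bias, and with infrequent bleeding it is small. The documents give no bleeding rates, spread, EDs per bleed or regimen split. The per-boy descriptive AsBR in Protocol 11.3.2.1 comes first, and the Poisson figure is an addition to it. Bleeds per person-time is also a recognised quantity. That the mean of per-boy rates is the target is an inference from the per-subject derivation, not something the plan states.

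Other exit routes weaken the link. Inhibitor-positive boys follow a different rule, preventive and additional doses also count as EDs, and Protocol 3.2.5 allows regimen switches. In a check at 20 bleeds a year, switching unrelated to bleeding (mean 2 years) brought pooled/true to 0.83 to 0.93, so the bias shrank but remained. Switching prompted by bleeding would again shorten heavy bleeders' on-demand time. The 6 years is an expectation, not a cap.

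The stakes are also limited. Regimens are assigned by investigators, no p-values are planned (Protocol 11.3), and the ratio is confounded by indication under any model. A shift towards 1 would make prophylaxis look less beneficial, not more.

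All of this stands. It limits the certainty and size of the point but does not remove it: the only planned CI and ratio for AsBR still come from the estimator exposed to the exit rule.

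**Conclusion.** The point holds for Arm 2, conditionally. If on-demand boys differ in bleeding rate and many reach 75 EDs before the study duration ends their follow-up, the Poisson on-demand AsBR tends to fall below the mean per-boy rate. The ratio then rises, which is towards 1 if the prophylaxis rate is the lower one. Under the stated assumptions the understatement runs from almost none to about 40%. The direction is well supported; the size cannot be fixed from the documents.

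It would be tempting to extend this to the previously treated patients leaving at 100 EDs. That is not worth pursuing: they stay for at least 100 EDs, Arm 1 counts EDs from earlier studies, and SAP 4.1.2 says their analysis was already complete. The change is worth making because it is cheap, not because a large bias has been shown.

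**What to change.** In Protocol 11.3.2.1 and SAP 4.6.1.1 and 4.13, for Arm 2 AsBR and ABR, take the rate, 95% CI and prophylaxis/on-demand ratio from one of these, named in advance:

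1. the mean of per-subject rates by regimen, with a bootstrap CI that resamples whole boys, so that switchers carry both regimens together; or
2. a negative binomial model with the same log-time offset (DIST=NEGBIN in GENMOD).

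Keep the pooled Poisson as a sensitivity analysis, and describe it as a person-time rate.

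If the negative binomial is chosen, state that it greatly reduces the bias but does not fully remove it. Exit depends on all EDs, whereas the AsBR model sees only spontaneous bleeds. With 20% of bleeds spontaneous, 12 boys and 12 to 30 bleeds a year, it averaged 0.92 to 0.97 of truth, while the per-boy mean stayed at 1.00 to 1.03.

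Cost: SAP wording and a small program change, with no new data. The CI will be somewhat wider, and the negative binomial may fail to converge in small rows, where the per-boy mean can serve as the fallback.
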